Closed squares show the results of subjects that were boosted on Day 28 after the first immunisation. Open squares depict PRNT levels of subjects that were boosted on day 90 after the first immunisation.

Safety Analysis:

Vital sign checks including measurement of blood pressure, pulse rate and axillary body temperature as well as physical examination were performed at all visits. Additionally, the injection site was inspected and evaluated for local side effects by the investigator at each visit and before and 6 hours after each vaccination. Grading of local pain, tenderness, redness, swelling, itching and induration was performed according to the respective FDA guidance for industry and the guidance of the Brighton Collaboration. Accordingly, local side effects were graded as mild (grade 1), moderate (grade 2), severe (grade 3) and potentially life-threatening (grade 4). All participants were provided with a template that allows estimation of local reactions (supplementary information).

Pain, itching and induration were graded as mild if they did not interfere with daily activity, as moderate if they did compromise activity or necessitated repeated use of non-narcotic pain reliever/anti-inflammatory and pain relieving ointment (itching and induration) and as severe if they prevented daily activity. Grade 4 pain/itching included the need for Emergency room (ER)

visit or hospitalisation. Swelling and erythema below a diameter of 5 cm were rated as mild. Swelling/erythema exceeding 10 cm in diameter were considered to be severe and necrosis indicated grade 4 swelling/erythema (supplementary information).

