10.1.6 Severity

AEs must be graded by a medically qualified person as being mild, moderate, severe or life-threatening and their approximate duration given. Definitions of severity are as follows:

Mild: an AE that requires minimal or no treatment and does not interfere with daily activities;

Moderate: an AE that is sufficiently discomforting to interfere with normal activities;

Severe: an AE that is incapacitating or prevents normal activities and may require systemic drug therapy or other treatment.

Potentially life threatening: an AE that requires immediate intervention to prevent death.

"life-threatening" refers to an AE in which the subject was at risk of death at the time of the event, it does not refer to an AE which hypothetically might have caused death if it were more severe.

Please see Appendix 1 for stencil to be used for grading local injection site reactions and Table 5 and 6 for grading of systemic and local reactions.

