10.2 Recording of Adverse Events

All AEs occurring during the treatment period starting after the first vaccination at Visit 1 until termination of Visit 5 (day 56) observed by the investigator or reported by the subject (verbally or in the subject diary), will be recorded, whether or not related to the study treatment.

AEs will be requested at each visit during the treatment period up to Visit 5 (day 56) and additionally solicited by a subject's diary for 7 days after each vaccination. (see section 11.7)

The subjects will be asked generally (e.g. "How are you?") as well as specifically (e.g. "Have you experienced any problems since the last visit?").

The investigator must record all adverse events in the eCRF. One single adverse event page must be used per adverse event, from start to resolution, stating the following information: AE description, date of onset and end date, severity, relatedness, seriousness and action taken. Please consider definitions of section 10.1. Follow-up information should be provided as necessary.

If possible, the investigator should record the diagnosis. If a diagnosis is not available, the investigator should record each sign and symptom as individual adverse events. However, as soon as a diagnosis becomes available, all signs and symptoms should be summarised and replaced by the underlying adverse event term (e.g. common cold instead of separate AEs for headache, rhinorrhoea, arthralgia, fever etc.)

The AE should be documented stating the highest severity (i.e. if an AE goes from mild severity to moderate severity or vice versa, the whole episode of the AE should be reported with the moderate severity). Please consider Table 5 and 6 for grading local injection site reactions and systemic reactions.

For causality reporting purposes, the categories "definitely", "probably" and "possibly" qualify an event as "suspected" adverse reaction. AEs with missing causality assessment will be regarded as possibly related unless further specified.

Any medical condition that is present at screening will be considered as medical history and not reported as an AE. However, if the subject's condition deteriorates at any time during the study, it will be recorded as an AE.

It will be left to the investigator's clinical judgment to decide whether an AE requires the subject's removal from the study. In case of discontinuation, the subject will undergo an early termination visit.

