11.7 Subject Diary

The subjects will be instructed to complete a diary for 7 days after each vaccination to document local and systemic tolerability as well as body temperature.

Solicited local and solicited systemic AEs will be assessed by the subjects themselves by checking for presence of the listed symptoms and measuring the size of the affected area where appropriate (a template will be provided for local reaction grading, as shown in Appendix 1). The diary will also provide space for recording unsolicited AEs and concomitant medication.

Recording should be done approximately at the same time each day, starting on the day of vaccination. The first entry should be made 6 hours ± 1 h after vaccination at Visit 1 and Visit 3.

The subjects' diaries will be collected and verified for completeness by the investigator at Visit 2 and Visit 4. Any AE recorded in the subject diaries will be entered in the eCRF by the investigator or authorised delegates. The investigator will re-evaluate the severity of the reported local and systemic AEs according to the below Tables 5 and 6.

Diary solicited systemic AEs include: nausea, vomiting, headache and fatigue, also to be documented in the eCRF.

In addition, body temperature will be recorded daily for 7 days and fever will be graded by the investigator according to the FDA Guidance for Industry. For details see below Table 6.

Table 5: Grading of Local Reactions

Local reaction to injectable product	Mild (grade 1)	Moderate (grade 2)	Severe (grade 3)	Potentially life threatening (grade 4)
Pain	Does not interfere with activity	Interfere with activity or repeated use of non-narcotic pain reliever	Prevents daily activity or repeated use of non-narcotic pain reliever	Emergency room (ER) visit or hospitalisation
Tenderness	Mild pain to touch	Pain with movement	Significant pain at rest	ER visit or hospitalisation
Erythema/ Redness¹	≤ 5 cm	5.1–10 cm	> 10 cm	Necrosis or exfoliate dermatitis
Swelling²	≤ 5 cm and does not interfere with activity	5.1–10 cm or interfere with activity	> 10 cm or prevents daily activity	Necrosis
Itching	Does not interfere with activity	Interferes with activity or repeated use of non-narcotic pain reliever	Prevents daily activity or repeated use of anti-inflammation and pain-relieving ointment	Emergency room (ER) visit or hospitalisation

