Induration¹	≤ 1 cm Does not interfere with activity	> 1 to < 3 cm Interferes with activity or repeated use of non-narcotic pain reliever	≥ 3 cm Prevents daily activity or repeated use of anti-inflammation and pain-relieving ointment	Not applicable

¹ In addition to grading the measured local reaction at the greatest single diameter, the measurement should be recorded as a continuous variable.

² Swelling should be evaluated and graded using the functional scale as well as the actual measurement.

Table 6: Grading of Systemic Reactions

Systemic Reaction (General)	Mild (grade 1)	Moderate (grade 2)	Severe (grade 3)	Potentially life threatening (grade 4)
Nausea/ vomiting	No interference with activity or 1-2 episodes/ 24 hours	Some interference with activity or >2 episodes/ 24 hours	Prevents daily activity, requires outpatient IV hydration	Emergency room (ER) visit or hospitalisation for hypotensive shock
Diarrhoea	2-3 loose stools or < 400 gms/ 24hours	4-5 stools or < 400-800 gms/ 24hours	6 or more watery stools or >800 gms/ 24 hours or requires outpatient IV hydration	ER visit or hospitalisation
Headache	No interference with activity	Repeated use of non-narcotic pain reliever >24 hours or some interference with activity	Significant; any use of narcotic pain reliever or prevents daily activity	ER visit or hospitalisation
Fatigue	No interference with activity	Some interference with activity	Significant; prevents daily activity	ER visit or hospitalisation
Myalgia	No interference with activity	Some interference with activity	Significant; prevents daily activity	ER visit or hospitalisation
Illness or clinical AE (as defined according to applicable regulations)	No interference with activity	Some interference with activity not requiring medical intervention	Prevents daily activity and requires medical intervention	ER visit or hospitalisation
Fever (°C)	38.0 - 38.4	38.5 - 38.9	39.0 - 40.0	>40.0

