6.2.2 Derivations and Definitions

- All solicited and unsolicited Adverse Events up to day 56 (Visit 5) will be analyzed for the preliminary analysis. AE reporting and documentation is completed at Day 56. Thus all AE in the database are considered for the adverse event endpoints. In case of unexpected data change, new reported AEs or follow-up information, affected tables and/or listings may be repeated for the final analysis. Otherwise,

Adapted from:

STAT03_A Statistical Analysis Plan

Version 6.0, Effective Date 16-Feb-2018

Confidential and intellectual property of Assign DMB. No part of this document or its contents may be duplicated, referenced, published or otherwise disclosed in any form or by any means without prior written consent of Assign DMB.

Page 16 of 29

06CJDX

adverse event tables are not repeated at the final analysis. This decision may be done in a DRM prior to database closure, see [Section 2.9](#).

- Percentages for AE rates are based on N (treatment group totals).
- Medical Conditions/symptoms noted prior to first IMP administration will be reported as medical history and not as adverse events. In case of an incomplete start date where it cannot clearly be decided if the Adverse Event started before the first IMP the Adverse Event will be considered to be started before first IMP.
- An Adverse Events is considered to be related to study treatment if “Relationship to Study Treatment” is answered with “definitely”, “probably” or “possibly” or the causality is missing.
- Adverse Events where an action was taken are considered if “Action taken with Study Treatment” is answered with “Second IMP Administration Delayed” or “Second IMP not Administered”.
- Tables showing “severe” events will include events with grade 3 or 4 or missing grade.
- In tables showing subjects with AEs by maximum severity, subjects will be counted only in the highest grading category, but events will be counted in each reported grading category.
- In tables showing AEs by causality, subjects will be counted only in the strongest relationship category, but events will be counted in each category.

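### Table 5 gives the same analgesic criterion for grade 2 and grade 3 injection-site pain, so pain with repeated non-narcotic use and no prevented activity has no unique grade

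*Combined protocol and SAP*

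**What the plan says.** Table 5 (protocol section 11.7) defines grade 2 injection-site pain as "Interfere with activity or repeated use of non-narcotic pain reliever" and grade 3 as "Prevents daily activity or repeated use of non-narcotic pain reliever". Use of the table is mandatory: "The investigator will re-evaluate the severity of the reported local and systemic AEs according to the below Tables 5 and 6".

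The general definition in protocol section 10.1.6 is "Severe: an AE that is incapacitating or prevents normal activities and may require systemic drug therapy or other treatment", with moderate meaning interference with normal activities. The same section then sends the grader to Tables 5 and 6 for local and systemic reactions.

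On recording, protocol section 10.2 states: "The AE should be documented stating the highest severity". On reporting, SAP section 6.2.2 says that tables of severe "events will include events with grade 3 or 4 or missing grade", and that tables by maximum severity count each subject once, in the highest category.

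**The concern.** A grading scale has to give one grade for one set of findings. In the Pain row the activity criteria are ordered (interferes, then prevents), but the analgesic criterion is repeated unchanged. No number of doses, duration or precedence rule separates the two uses. Two investigators could grade the same diary entry differently, and both would be following the table.

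The boundary at issue is the one between moderate and severe, which the SAP uses to define its severe tables. Safety is part of the primary objective (protocol section 5.1) and the rate of solicited AEs is a secondary endpoint (protocol section 6.2.2). Pain is also a common reaction: phase I reported injection-site pain in 50.0% of subjects (protocol section 4.4.1). If the row stays as it is, part of the severe count for local reactions will reflect how the overlap was resolved and not how bad the pain was.

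**Working it through.** The plan states no severe-AE rate and made no formal sample size calculation, so there is no figure to reproduce. The check compares the texts and then works out what one ambiguous subject is worth.

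**Step 1. The texts side by side**

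| Source | Moderate / grade 2 | Severe / grade 3 | Overlap? |
|---|---|---|---|
| Table 5, Pain | "Interfere with activity or repeated use of non-narcotic pain reliever" | "Prevents daily activity or repeated use of non-narcotic pain reliever" | Yes, analgesic clause |
| Protocol 10.1.6, general | Interference with activities | Incapacity or prevented activities | No |
| Table 6, Headache | Repeated non-narcotic use beyond 24 hours, or some interference | "Significant; any use of narcotic pain reliever or prevents daily activity" | No |
| Protocol 4.4.1, phase I grading | "as moderate if they did compromise activity or necessitated repeated use of non-narcotic pain reliever/anti-inflammatory and pain relieving ointment (itching and induration") | Prevented daily activity | No |

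**Step 2. Which events are ambiguous**

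- Pain without repeated analgesic use is graded on activity alone.
- Pain that prevents daily activity reaches grade 3 on that criterion.
- Pain leading to an emergency room visit or hospitalisation is grade 4.
- Pain with repeated non-narcotic use, without prevented activity and not grade 4, meets grade 2 and grade 3 by the same clause. Only this subset has no unique grade.

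**Step 3. Is there a tie-break?** Protocol section 10.2 explains its highest-severity rule with an AE that moves between mild and moderate over its course, so the rule concerns change over time. The SAP section 6.2.2 rule takes a maximum over a subject's graded events. Both rules start from grades already assigned. Section 10.1.6 separates the grades but refers to Table 5 without saying which governs.

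**Step 4. Outputs reached.** SAP Tables 1.4.2, 1.4.3 and 1.4.4 (severe rows for all, solicited and solicited local AEs), Tables 1.4.7, 1.4.10 and 1.4.11 (maximum severity), and the severe solicited AE listings. Solicited systemic Table 1.4.5 and the unsolicited severe tables are not reached.

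**Step 5. Effect per subject.** Inputs: 12 per group and 60 in all (protocol Table 1). For a subject with no other severe event, moving between grade 2 and grade 3 changes:
- the group's severe rate by 1/12 = 8.3 percentage points
- the overall rate by 1/60 = 1.7 percentage points

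**Step 6. Range under stated assumptions.** The documents do not give the share of subjects in the ambiguous subset. Assume that pain prevents daily activity in 5%, and that 0–30% fall in the ambiguous subset.
- Narrow reading (ambiguous events graded 2): severe pain 5%; 12 × 0.05 = 0.6 expected per group.
- Wide reading (graded 3): 5% to 35%; 0.6 to 12 × 0.35 = 4.2 expected per group.
- With 10% ambiguous, the chance of at least one severe pain in a group of 12 is 1 − 0.95^12 = 0.46 on the narrow reading and 1 − 0.85^12 = 0.86 on the wide one.

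**Step 7. Effect on the Fisher tests.** As a pairwise illustration, two-sided, against a group with 0/12:

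| Severe in the other group | p |
|---|---|
| 1/12 | 1.00 |
| 2/12 | 0.478 |
| 3/12 | 0.217 |
| 4/12 | 0.093 |
| 5/12 | 0.037 |

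Reclassification alone would need five subjects in one group and none in the other to reach p < 0.05.

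**The case against.** The best defence is that the practical effect is small. The subset is narrow, and section 10.1.6 gives an investigator a way to separate the grades. Grading is done by blinded assessors at one site, so a grading habit should not differ systematically between groups. The safety analysis is descriptive with supplementary Fisher tests, and step 7 shows that those tests are not easily moved. The individual stopping rule for solicited reactions (protocol section 8.9.1) uses grade 4 systemic reactions. All of this stands and limits the size of the point. It does not supply the missing rule, and blinding does not make two readings of one cell agree.

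Three stronger readings are tempting, and the documents do not support them.

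- *The highest-severity rule makes these events grade 3, so severe rates are inflated.* As step 3 shows, neither rule is written as a tie-break. Grade 2 is equally open, so upward bias is conditional on the choice made.
- *The artefact could match the whole severe count of phase I.* One might take 50.0% of 60 = 30 subjects with pain, suppose that 10–30% of them use analgesics repeatedly, and reach 3–9 subjects against six with severe AEs in phase I. The 10–30% has no source in the documents. Six of 42 scales to 6/42 × 60 = 8.6 per 60, so only the top of the range comes near it. Phase I also injected up to 1 mL, and section 4.4.1 links its dose-dependent local reactions to that volume; this trial gives 0.4 ml.
- *The Itching and Induration rows have the same fault.* Their grades 2 and 3 name different treatments, so no treatment criterion is repeated. They differ from the phase I grading, but section 11.6 describes the present scale as modified, and a difference from a completed study is not an internal contradiction.

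**Conclusion.** The point holds for the Pain row of Table 5. Injection-site pain with repeated non-narcotic use, without prevented daily activity and not grade 4, has no unique grade, and no section of the protocol or SAP resolves it. A reader might infer that the severe-AE rate as a whole is undefined. It is not: other pain, the other AE terms and the systemic and unsolicited severe tables are untouched by this overlap.

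The firm size is 8.3 percentage points on a group's severe rate and 1.7 on the overall rate for each subject graded one way or the other. This assumes full groups of 12 and no other severe event in that subject. The number of such subjects cannot be derived from the documents; the range in step 6 rests on assumed shares. The primary endpoint, the significance level and the grade 4 stopping rule do not depend on the point. It is a drafting ambiguity in a rule that the trial applies, and worth correcting because it sits on the boundary that defines severe.

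**What to change.** Make the Pain grades in Table 5 mutually exclusive, so that any combination of activity limitation and analgesic use leads to one grade. Reconcile the row with section 10.1.6 and the headache row of Table 6, note how phase I graded pain in section 4.4.1, and state which text governs if they differ. Which grade the criterion belongs to is for the sponsor to decide; this review takes no position.

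Use the same wording in the subject diary, the eCRF guidance and the instructions for investigator re-grading. Settle it before grading starts, or at the latest before the Blind Data Review Meeting (SAP section 2.9). If some events have already been graded, apply the settled rule to all of them while still blinded.

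The cost is a table correction in the protocol and matching eCRF guidance. No new data are needed; the diary already has space for concomitant medication.

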Furthermore, participants were requested to keep a study diary in order to record all local and systemic symptoms and any adverse event occurring during the first two weeks after vaccination starting with the first entry 6 hours (± 1) after vaccination. The subjects themselves recorded the assessments once daily at the same time each day. Completeness and accuracy of self-reported symptoms and side effects were verified at each visit by a study-related physician. Diaries were reviewed together with the particular participant at each visit and participants were interviewed for any adverse events. Diaries had to be signed by both the particular participant and the reviewing physician at the end of each vaccination period to confirm and ensure completeness and reliability of self-reporting. The investigator collected the diaries at each visit and new ones were dispensed after vaccination.

Solicited and non-solicited adverse events (AEs) were reported separately. Solicited AEs included pyrexia, flu like illness, headache and injection-site- related side effects (erythema, swelling, induration and pain).

In general, MV-CHIK vaccine had an acceptable tolerability profile. All adverse events observed were treatment emergent AEs and were recovered without any sequelae before or at study end.

The most frequently solicited AEs were headache (57.1%), injection site pain (50.0%), influenza like illness (45.2%), vaccination site pain (40.5%), fatigue (38.1%), nausea (31.0%), myalgia (26.2%) and arthralgia (23.8%). The most frequently related solicited AEs were injection site pain (50.0%), vaccination site pain (40.5%), headache (28.6%) and fatigue (23.8%).

Unsolicited AEs were AEs with none of the preferred terms of solicited AEs. 28 subjects (66.7%) had a total of 73 unsolicited AEs. Two subjects (4.8%) had two severe unsolicited AEs, five subjects (11.9%) had seven related unsolicited AEs and 19 subjects (45.2%) reported 33 unsolicited AEs where an action was taken. Two subjects (4.8%) reported two serious unsolicited AEs. The most frequently unsolicited AEs were nasopharyngitis (26.2%) and oropharyngeal pain (11.9%).

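### Table 5 lists repeated non-narcotic analgesic use under both grade 2 and grade 3 pain, so one defined subset of injection-site pain has no single grade

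*Combined protocol and SAP*

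**What the plan says.** Protocol section 11.7, Table 5, Pain row:

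- Grade 2 (moderate): "Interfere with activity or repeated use of non-narcotic pain reliever".
- Grade 3 (severe): "Prevents daily activity or repeated use of non-narcotic pain reliever".
- Grade 4: an emergency room visit or hospitalisation.

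The table is binding on the site. On diary entries, the same section states: "The investigator will re-evaluate the severity of the reported local and systemic AEs according to the below Tables 5 and 6".

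Protocol section 12.3 summarises solicited events by grade and treatment group. SAP section 6.2.2 counts grade 3, grade 4 and missing grade as severe.

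**The concern.** A grading scale should place each clinical state in one grade. Here two adjacent grades share a criterion that is sufficient on its own. Two investigators who both follow the protocol can give the same subject different grades, and the boundary in question is the one that decides whether an event is counted as severe.

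The symptom is a common one. Protocol section 4.4.1 reports injection site pain in 50.0% of phase I subjects and vaccination site pain in 40.5%, the two most frequent related solicited events. Safety is part of the primary objective (section 5.1), and adverse event rates are the first secondary endpoint (section 6.2.2). At stake is whether the severe-reaction counts in this trial have a fixed meaning.

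**Working it through.** The plan has no figure of its own to reproduce: section 12.4 says that no formal sample size calculation was done, and no analgesic-use rate is given. The check is a comparison of texts, followed by arithmetic for scale.

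**1. Which cases are ambiguous.** Let I = interferes with activity, P = prevents daily activity, R = repeated non-narcotic analgesic use. Grade 2 is (I or R) and grade 3 is (P or R).

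- R absent: activity alone decides between the two grades.
- P present: the activity criterion already supports grade 3.
- Emergency visit or hospitalisation: grade 4.
- R present, P absent, no emergency visit or hospitalisation: both grade 2 and grade 3 are met.

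Only the last case is ambiguous.

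**2. Is there a tie-break?** Section 10.2 says "The AE should be documented stating the highest severity", but explains this by an event that moves between mild and moderate. It covers change over time, not one state that satisfies two definitions. Applied here regardless, it would leave the grade 2 analgesic criterion without effect. The maximum-severity rule in SAP section 6.2.2 operates on grades already assigned. Neither resolves the overlap.

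**3. Comparison with the rest of the protocol.**

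- Section 10.1.6 defines severe by incapacity or loss of normal activity. Drug therapy is something that a severe event may require, not a criterion sufficient by itself. The grade 3 pain cell is in tension with this, although 10.1.6 also sends graders to Tables 5 and 6.
- Section 4.4.1 describes phase I pain, itching and induration "as moderate if they did compromise activity or necessitated repeated use of non-narcotic pain reliever/anti-inflammatory", with severe reserved for prevented daily activity.
- The headache row of Table 6 puts repeated non-narcotic use in grade 2. Its grade 3 cell reads "Significant; any use of narcotic pain reliever or prevents daily activity". The two cells are distinct.
- The itching row of Table 5 also changes its treatment criterion between grades. Its grade 3 cell reads "Prevents daily activity or repeated use of anti-inflammation and pain-relieving ointment".

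No other row of Table 5 or 6 repeats a grade 2 criterion word for word under grade 3.

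**4. Where the grade goes.** Injection-site pain is a local solicited event. It feeds the severe and related-severe rows of SAP Tables 1.4.2, 1.4.3 and 1.4.4, and the maximum-severity Tables 1.4.7, 1.4.10 and 1.4.11. Table 1.4.5 is restricted to systemic events and is not touched.

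**5. Size.** One subject in 12 is 1/12 = 8.3 points of a group's rate; one in 60 is 1.7 points overall.

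For the number of subjects, let p be the share with pain and q the share of pain cases that are ambiguous. The expected shift in the severe rate is s = p × q, which is 12s subjects per group. The chance of at least one ambiguous case in a group is 1 − (1 − s)^12. I take p = 0.405 to 0.50, using the two phase I rates (17/42 and 21/42) as a working range. The range q = 0.05 to 0.50 is an assumption.

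| p | q | s | Subjects per 12 | Chance of at least one in a group |
|---|---|---|---|---|
| 0.405 | 0.05 | 0.020 | 0.24 | 22% |
| 0.50 | 0.05 | 0.025 | 0.30 | 26% |
| 0.405 | 0.50 | 0.203 | 2.43 | 93% |
| 0.50 | 0.50 | 0.250 | 3.00 | 97% |

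Over all 60 subjects the range is 60s = 1.2 to 15.

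**The case against.** The strongest case on the other side accepts the overlap and disputes its weight.

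- **Consequences are limited.** The primary endpoint is PRNT₅₀. The grade-based individual stopping rule in section 8.9.1 concerns grade 4 systemic reactions, and no study-level rule uses grade 3 pain. All arms share one scale applied by blinded assessors, so the result is misclassified severity rather than an evident bias between groups. This stands.
- **The upper end of the range may be too high.** Section 4.4.1 says that 82% of limb pain associated with injection was graded mild. On the phase I scale, repeated analgesic use made pain at least moderate. If that figure carries over to injection-site pain, at most 18% of cases could be in question: 0.18 × 12 × 0.405 to 0.50 = 0.9 to 1.1 subjects per group, or 7 to 9 points. The passage concerns musculoskeletal pain, so the transfer is itself an assumption, but it is a good reason not to rely on 3 subjects or 25 points.
- **Phase I is an imperfect guide.** It used three injections, volumes up to 1 mL and two-week diaries; this trial uses two 0.4 ml injections and 7-day diaries. The two phase I rates are separately reported terms, not limits of one estimate. Section 11.6 calls the present scale modified, so a difference from phase I is not in itself an error. Neither document plans a comparison of severe-pain rates with phase I. All of this stands.

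Three stronger readings are tempting. A reader might infer that injection-site pain as a whole cannot be graded, but step 1 shows that only one subset is affected. A reader might infer that section 10.2 forces grade 3, but that rule is about events that change over time. A reader might infer that Fisher tests on every severity table are affected. However, SAP section 6.2.1 attaches the test to the adverse event overview and protocol section 12.3 to summary tables; no test is specified for Tables 1.4.10 and 1.4.11.

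What the objection does not remove is the duplicated criterion or the absence of a tie-break.

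**Conclusion.** The Pain row is wrong as written, at moderate to low severity. The overlap and the missing tie-break follow from the text alone and need no assumption. The row reads cleanly and its neighbours are intact, so an extraction fault is unlikely, though the source page should be checked.

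The effect of one reclassified subject is certain, given groups of 12. The number of such subjects is not known: 0.2 to 3 per group depends entirely on the assumed pain rate and ambiguous share, and the low end is as compatible with the documents as the high end. The documents do not support a claim that the comparison between groups is biased, or that the primary analysis or any stopping decision is at risk.

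**What to change.** Reconcile the two Pain cells with each other, with section 10.1.6 and with the phase I description in section 4.4.1, so that each criterion appears in one grade only. Which grade should hold the analgesic criterion is for the sponsor and the investigator to settle. Carry the reconciled wording into the eCRF and any diary grading text.

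If diaries have already been graded, re-check the affected cases, blinded, against the recorded concomitant medication, and finish before the Blind Data Review Meeting (SAP section 2.9), because the preliminary analysis that follows it is unblinded.

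The cost is one table row in a protocol amendment and the matching form text. Medication is already captured in the diary (section 11.7) and, with dates and reasons, in the eCRF (section 9.10.1), so new data collection should not be needed. The diary itself is not among the documents, so this should be confirmed.
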